9.3.2.2 Analysis of Secondary Endpoints

9.3.2.2.1 Analysis of Key Secondary Efficacy Endpoints

Absolute and percentage change from baseline in exercise duration during CPET at Week 24

Analysis of these two variables will be similar to that of the primary analysis of the primary efficacy endpoint using a mixed model repeated measures (MMRM) using SAS PROC MIXED based on the FAS, with the exception that exercise duration during CPET at baseline will replace baseline VO_2 max value in the MMRM model.

Absolute and percentage change from baseline in exercise duration measured in the unit of seconds at both Week 12 and Week 24 will be derived from the main model based on the FAS. The LS means (with 95% CI) at each visit will be plotted by treatment groups.

In addition, raw changes from baseline in exercise duration measured in the unit of seconds as well as raw values at both Week 12 and Week 24 will be summarized using descriptive summary statistics.

9.3.2.2.2 Analysis of Additional Secondary Efficacy Endpoints

Analysis of the following other secondary endpoints will also be similar to that of the primary analysis of the primary efficacy endpoint using a mixed model repeated measures (MMRM) using SAS PROC MIXED based on the FAS, with the exception that for each of these secondary endpoints, their corresponding value at baseline will replace baseline VO_2 max value in the MMRM model.

- Absolute change from baseline in VO_2 max during cardiopulmonary exercise testing (CPET) at Week 24
- Absolute and relative change from baseline in oxygen consumption (VO_2) at anaerobic threshold (AT) (the point during exercise at which lactate starts to accumulate) at Week 24
- Absolute and relative change from baseline in percent predicted forced expiratory volume in 1 second (ppFEV₁) at Week 24. Note: Baseline ppFEV₁ will not be included in the MMRM model because ppFEV₁ at baseline as a stratification factor has already been included in the model.
- Absolute and relative change from baseline in body mass index (BMI) at Week 24

- Absolute change from baseline in Cystic Fibrosis Questionnaire-Revised (CFQ-R) respiratory domain score at Week 24
- Absolute and relative change from baseline in functional VO_2 gain at Week 24
- Absolute and relative change from baseline in the slope of pulmonary ventilation (VE) versus carbon dioxide production (VCO_2) at Week 24

Absolute and percentage change from baseline in these other secondary endpoints above at both Week 12 and Week 24 will be derived from the main model based on the FAS.

In addition, raw changes from baseline in these other secondary endpoints above as well as raw values at both Week 12 and Week 24 will be summarized using descriptive summary statistics.

Analysis of the following other secondary endpoints will be based on descriptive summary statistics only. Descriptive summary statistics along with 95% confidence interval will be provided at both Week 12 and Week 24 by treatment groups.

- Absolute change from baseline in overall Patient Health Questionnaire (PHQ-8) and Generalized Anxiety Disorder (GAD-7) scores at Week 24
- Proportion of patients in each severity category of PHQ-8 and GAD-7 scores at both baseline and Week 24.
- Absolute and relative change from baseline in physical activity as determined by actigraphy at Week 24
- Absolute and relative change from baseline in duration of sleep time during the night at Week 24
- Absolute and relative change from baseline in time above sedentary duration at Week 24

In addition, raw values from baseline in these other secondary endpoints above as well as raw values at both Week 12 and Week 24 will be summarized using descriptive summary statistics.

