9.1 Inclusion Criteria

Subjects who meet all of the following inclusion criteria will be eligible:

1. Subject (or their legally appointed and authorized representative) will sign and date an informed consent form (ICF), and where appropriate, assent form.
2. Willing and able to comply with scheduled visits, treatment plan, study restrictions, laboratory tests, contraceptive guidelines, and other study procedures.
3. Subjects (male and female) will be at least 12 years old on the date of informed consent.
4. Homozygous for the *F508del-CFTR* mutation (as documented in the subject's medical records or from genotyping performed during screening).

5. Confirmed diagnosis of CF⁴⁴ defined as a sweat chloride value ≥ 60 mmol/L by quantitative pilocarpine iontophoresis, as documented:
 - in the subject's medical records **OR**
 - from sweat chloride test result obtained during screening (to be conducted only if the subject does not have a sweat chloride test result in the medical records).
6. Stable CF disease as judged by the investigator.
7. FEV₁ at least 40% and not greater than 90% of predicted.
8. Willing to remain on a stable CF medication regimen through the Safety Follow-up Visit.

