7.3 Randomization

A total of approximately 66 subjects (33 per arm) who meet eligibility criteria will be stratified by age (<18 versus \geq 18 years of age), sex (male versus female), and percent predicted FEV₁ severity determined at the baseline Visit (<70 versus \geq 70), and then randomized (1:1) to 1 of the 2 treatment arms.

The randomization codes were produced by a designated vendor [REDACTED]. In order to protect the study blind and maintain the scientific integrity of the data, 1 Vertex biostatistician and 1 [REDACTED] biostatistician were involved in the randomization process for each study: a Vertex biostatistician who is blinded to the actual treatment code and a [REDACTED] unblinded biostatistician who is not associated with the study. Below is a brief description of the randomization process.

- The Vertex biostatistician created the randomization specification.
- The external designated vendor [REDACTED] created the dummy randomization code, which was reviewed and approved by the Vertex biostatistician.
- After approval, the external designated vendor generated the production randomization list and provided it to the unblinded [REDACTED] biostatistician for review.
- After all outstanding issues were resolved; the external designated vendor generated the final randomization list and provided it to the unblinded [REDACTED] biostatistician to upload in the designated final randomization study area.

The unblinded [REDACTED] biostatistician provided the final randomization list to the interactive web response system (IWRS) vendor. A copy of the final randomization list, provided in sealed tamper-evident envelopes, was archived at Vertex.

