9.2.2 Demographics and Baseline Characteristics

Demographic data will be summarized based on the FAS:

- Age
- Age groups (< 18 and ≥18 years)
- Sex (female and male)
- Ethnicity

- Race

Baseline characteristics will be summarized based on the FAS:

- Weight (kg)
- Weight z-score (subjects ≤ 20 years old) Weight, adjusted for age and sex, will be analyzed as weight-for-age z-score (weight z-score). The calculation of weight z-score is similar to that of BMI z-score (using the CDC growth charts and the derivation described). Using the same equation as in the CDC growth charts and the derivation described in the website below, X in the equation is the collected weight and L , M , and S parameters are selected from the CDC weight-for-age chart. The WTAGE file contains these parameters by sex and age; it is available at the website http://www.cdc.gov/growthcharts/percentile_data_files.htm. NOTE: The CDC growth charts are designed for use in pediatric populations (2 to 20 years of age); therefore, weight z-score will be calculated only for subjects in this age range.
- Height (cm)
- Height z-score (subjects ≤ 20 years old) Height, adjusted for age and sex, will be referred to as height-for-age z-score (or height z-score). The calculation of height z-score is similar to that of BMI z-score (using the CDC growth charts and the derivation described). Using the same equation as in the CDC growth charts and the derivation described in the website below, X in the equation is the collected height and L , M , and S parameters are selected from the CDC height-for-age chart. The STATAGE file contains these parameters by sex and age; it is available at the website http://www.cdc.gov/growthcharts/percentile_data_files.htm. NOTE: The CDC growth charts are designed for use in pediatric populations (2 to 20 years of age); therefore, height z-score will be calculated only for subjects in this age range.
- BMI (kg/m^2)
- BMI z-score (subjects ≤ 20 years old)
- Percent predicted FEV₁ at screening (<70, ≥ 70)
- Percent predicted FEV₁ at baseline (<40, ≥ 40 to <70, ≥ 70 to ≤ 90 , >90)
- Percent predicted FEV₁ at baseline
- FEV₁ (L)
- FVC (L)
- Percent predicted FVC
- FEF_{25-75%} (L/sec)
- Percent predicted FEF_{25-75%}
- FEV₁/FVC
- VO₂max
- Exercise duration during CPET

- Oxygen consumption (VO_2) at anaerobic threshold (AT) (the point during exercise at which lactate starts to accumulate)
- Functional VO_2 gain

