9.3.1.2 Primary Analysis of Primary Efficacy Endpoint

The primary analysis for the primary efficacy endpoint will be based on a mixed model repeated measures (MMRM) using SAS PROC MIXED based on the FAS.

The model, including percentage change from baseline in $VO_2\text{max}$ (including all measurements up to Week 24 [inclusive], both on-treatment measurements and measurements after treatment discontinuation) as the dependent variable, treatment, visit, and treatment-by-visit interaction as fixed effects, with adjustment for sex (male versus female), age group at baseline (<18 versus \geq 18 years old), percent predicted FEV₁ at baseline (<70

versus ≥ 70), baseline $VO_2\text{max}$ value and subject as a random effect will be used to test the difference between active treatment group versus placebo. The primary result obtained from the model will be the treatment effect at Week 24.

Descriptive summary statistics including number of subjects, mean, standard error, and least-square means (LS means) along with the P values will be provided. In particular, the difference in LS means as well as LS means within each group and the corresponding 95% CI will be provided along with the P values to assess the treatment difference between placebo and lumacaftor in combination with ivacaftor. Additionally, the P value testing the treatment-by-visit interaction will be provided to assess the consistency of treatment effect over different visits.

The repeated-measures analysis will be based on the restricted maximum likelihood method assuming an unstructured covariance structure to model the within-subject errors. A Kenward-Roger approximation will be used for the denominator degrees of freedom. If there is a convergence problem due to the unstructured covariance matrix, a compound symmetry covariance structure will be used to model the within-subject errors. With a mixed effects model as the primary analysis model based on restricted maximum likelihood estimation and assuming that conditional on fixed and random effects, data are missing at random, no imputation of missing data will be done.

In addition, raw values of percentage change from baseline in $VO_2\text{max}$ at Week 24, and raw values of percentage change from baseline in $VO_2\text{max}$ at Week 12 will be summarized descriptively (number, mean, SE, SD, median, min, and max).

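### The ppFEV₁ models alone leave out their own continuous baseline, on the ground that a two-level ppFEV₁ stratum is already fitted

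*SAP*

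**What the plan says.** SAP 9.3.2.2.2 sets a general rule for the other secondary endpoints analysed by MMRM: "their corresponding value at baseline will replace baseline" VO₂max in the model. SAP 9.3.2.2.1 does the same for the key secondary endpoint, where "exercise duration during CPET at baseline will replace baseline" VO₂max. The primary model in SAP 9.3.1.2 carries baseline VO₂max.

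One exception is written into SAP 9.3.2.2.2, for absolute and relative change in ppFEV₁: "Baseline ppFEV₁ will not be included in the MMRM model because" ppFEV₁ "at baseline as a stratification factor has already been included in the model".

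The factor meant is dichotomous. In SAP 9.3.1.2 the adjustment term is "percent predicted FEV₁ at baseline (<70" against ≥70. SAP 7.3 stratifies on "percent predicted FEV₁ severity determined at the baseline Visit" with the same cut. Protocol 9.1 admits subjects with FEV₁ "at least 40% and not greater than 90% of predicted". SAP 9.2.2 tabulates baseline ppFEV₁ as a continuous variable and in four categories, beginning "Percent predicted FEV₁ at baseline (<40" and ending above 90.

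PHQ-8, GAD-7 and the actigraphy endpoints are descriptive only. ppFEV₁ is therefore the only modelled endpoint without its own continuous baseline.

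**The concern.** The reason given treats a binary split as if it were the measurement. Within the entry range the lower stratum spans 70 − 40 = 30 points and the upper 90 − 70 = 20 points. The model treats a subject at 42 and a subject at 69 as having the same baseline.

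Subtracting baseline to form a change score does not remove this. Lung function measured twice regresses to the mean, so change stays negatively related to baseline within each stratum. For relative change the link is stronger, because baseline is also the denominator (SAP 9.1). If the arms differ by chance in baseline ppFEV₁ within strata, part of that difference appears as treatment effect.

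At stake are two non-key secondary estimates. They matter for interpretation: Protocol 5.1 raises the possibility that exercise gains are independent of FEV₁, so readers will set the ppFEV₁ effect beside the VO₂max effect, and the two would be adjusted differently.

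The Note also leaves a gap. It cancels the replacement of baseline VO₂max by baseline ppFEV₁ but does not say whether baseline VO₂max then stays in the ppFEV₁ model.

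**Working it through.** **The plan's own figure.** The only sample size stated is for the primary endpoint: difference 7.5%, SD 10%, two-sided 0.05, 80% power, 10% dropout (SAP 7.2). A two-sample t-test needs 29 per arm, and 29/0.9 = 32.2, rounded up to 33. The same method reproduces all six rows of SAP Table 7-1. The check below uses 30 completers per arm, since 33 × 0.9 = 29.7.

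**What the stratum leaves unadjusted.** The documents give no distribution for ppFEV₁, so one must be assumed. The simplest is uniform on 40–90:
- Total variance = 50²/12 = 208.3.
- Within-stratum variance = 0.6 × 30²/12 + 0.4 × 20²/12 = 45.0 + 13.3 = 58.3, an SD of 7.6 points.
- Share explained by the split = 1 − 58.3/208.3 = 72%.

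For a normal distribution with SD 14 and mean 60, 65 or 70, truncated to 40–90, the split explains 59% to 68% and the within-stratum SD is 6.5 to 7.4. Overall, 28% to 41% of baseline variance is left unadjusted.

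**Simulation.** Screening, baseline and Week 24 ppFEV₁ were taken as equally correlated normal variables with mean 65, SD 12 or 14, and correlation 0.80, 0.90 or 0.95. Eligibility of 40–90 was applied at screening. Each setting had 4,000 trials of 60 completers, allocated 1:1 within baseline stratum, with no true effect. A single-visit ANCOVA with treatment, stratum, sex and age group stood in for the MMRM, with and without continuous baseline.

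*Size of a chance imbalance.* SD of the arm difference = within-stratum SD × √(2/30). The within-stratum SD was 6.8 to 7.8 points (6.75 before rounding at the low end):
- 6.75 × 0.258 = 1.74
- 7.8 × 0.258 = 2.01

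That is about 1.7 to 2.0 points.

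*Shift in the estimate* = within-stratum slope of change on baseline × imbalance:

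| Endpoint | Slope | Shift at a 1-SD imbalance |
|---|---|---|
| Absolute change | −0.07 to −0.27 | 0.07 × 1.74 = 0.12 to 0.27 × 2.01 = 0.54 points |
| Relative change | −0.13 to −0.54 | 0.13 × 1.74 = 0.23 to 0.54 × 2.01 = 1.09 percentage points |

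For scale, the mean SE without the covariate was 0.98–2.23 points (absolute) and 1.59–3.73 percentage points (relative).

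*Change in SE when continuous baseline is added:*

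| Correlation | Absolute change | Relative change |
|---|---|---|
| 0.80 | −1.8% to −2.0% | −3.2% to −3.7% |
| 0.90 | −0.4% to −0.8% | −1.2% to −1.9% |
| 0.95 | +0.1% to +0.2% | −0.3% to −0.5% |

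*Validity without the covariate.* Type I error was 4.2% to 5.6%, and the mean estimate was within 0.04 of zero.

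**Second set of assumptions.** Here baseline was uniform on 40–90, the slope of absolute change on baseline was fixed at 0, −0.1, −0.2 or −0.3, and the residual SD was 6 or 8. The imbalance SD is 7.6 × 0.258 = 1.97 points. With non-zero slopes, the treatment estimate without the covariate followed the imbalance with a slope of −0.11 to −0.33. With the covariate, across all settings, that dependence was −0.03 to +0.01. At slope −0.3 and residual SD 6 the mean SE fell from 1.653 to 1.556 (−5.9%). At slope −0.1 there was no gain (1.555 against 1.557). Type I error was about 5% for both models.

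**The case against.** The strongest reply is that the analysis is valid as written and little changes. The estimate is unbiased over randomisation and type I error holds. The gain in precision for absolute change runs from nothing to about 2% in the main simulation. In a rerun under no effect, the two models disagreed on significance in only about 1.6–2.1% of trials. These are two endpoints outside any multiplicity control. All of this stands and limits the weight of the point.

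Second, the exception is deliberate and closer to the protocol. Protocol 12.3.3.1 has no continuous baseline for any endpoint, and 12.3.3.2 asks for similar analyses of the rest. That is true, so this is not a protocol departure. But the SAP chose to add each endpoint's baseline, and the reason it gives for stopping at ppFEV₁ does not hold.

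Third, the change score already subtracts baseline and the stratum absorbs much of the remainder. This is also true. What is left is the slope times the within-stratum imbalance, which is the quantity calculated above.

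Fourth, the two models' estimates typically differ by 0.18–0.28 SE for absolute change, but part of this is only the cost of estimating one more slope. With a true slope of zero they still differ by 0.13–0.14 SE. At correlation 0.95, where the difference is about 0.18, noise accounts for 0.13²/0.18² = 52% of its variance or more. That difference should not be read as imbalance corrected.

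Finally, a chance imbalance would be visible in the baseline table, and the <40 and >90 categories there do not prove that such subjects will occur. Both are fair, but seeing an imbalance is not adjusting for it, and the argument needs only the 40–90 range.

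**Conclusion.** The concern holds. The SAP's stated reason does not support the exception: a two-level factor is not the continuous baseline, and nothing prevents fitting both. No other section repairs it.

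The consequence is conditional. Given a chance within-stratum imbalance of about 1.7–2.0 points, the ppFEV₁ estimate shifts by about 0.1–0.5 points (absolute) or 0.2–1.1 percentage points (relative). There is no average bias and no inflation of type I error, and any precision gain is small: for absolute change up to 2% in the main simulation and about 6% at the steepest slope tried, sometimes nil, and for relative change up to 3.7%.

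These sizes rest on an assumed mean, SD, correlation and slope for ppFEV₁, on 60 completers, and on a single-visit model in place of the MMRM. The textual finding does not depend on them. The change is worth making because it costs almost nothing, but it does not touch the trial's main conclusion.

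**What to change.** Before unblinding, delete the Note on baseline ppFEV₁ in SAP 9.3.2.2.2. Fit continuous baseline ppFEV₁ together with the <70/≥70 stratum in the MMRMs for absolute and for relative change in ppFEV₁. The general rule then applies to ppFEV₁ as to every other modelled secondary endpoint, and baseline ppFEV₁ replaces baseline VO₂max, which closes the gap over which covariate the model carries.

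The cost is one deleted sentence, one covariate already collected and summarised under SAP 9.2.2, and one degree of freedom. SAP section 4 has the plan finalised before data lock and unblinding. A change made in that window cannot be taken as a response to the results.

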8.2 Rationale for Study Design and Study Drug Regimens

8.2.1 Study Design

This study is designed to evaluate the effect of LUM/IVA therapy on exercise tolerance in subjects with CF after up to 24 weeks of LUM/IVA therapy. CPETs will be used to assess improvements in exercise tolerance, as measured by VO_{2max} .

The use of a placebo control group is deemed necessary because exercise tolerance can be affected by a number of factors, including activity level, and subject activity may increase as a result of being involved in an exercise tolerance study.

This study will only enroll subjects who have not previously been exposed to LUM or IVA, and all subjects will continue their normal, stable treatment for CF throughout the study.

The study population will be subjects with CF who are 12 years of age and older and are homozygous for the *F508del-CFTR* mutation. Efficacy, safety, and pharmacokinetic profiles for LUM/IVA therapy were established in subjects 12 years of age and older with CF homozygous for the *F508del-CFTR* mutation in Studies VX12-809-103 (Study 103) and

VX12-809-104 (Study 104). Furthermore, this is the population for which LUM/IVA treatment has been approved in Europe and in the US.

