8.2.3 Rationale for Study Assessments

CPET: Maximal cardiopulmonary exercise testing that incorporates measurements of gas exchange provides precise measurements of exercise tolerance. This assessment provides several parameters of exercise tolerance and aerobic fitness including VO_2 , functional VO_2 gain, VCO_2 , AT, and VE. Functional VO_2 gain relates oxygen uptake to total ventilation during exercise and is an index of cardiopulmonary reserve. The VE versus VCO_2 slope is a measure of ventilatory efficiency. The AT is the exercise intensity at which lactate starts to accumulate.

Spirometry: Because lung disease is the major cause of morbidity and mortality for patients with CF, FEV₁, as measured by spirometry, is the most widely implemented standardized assessment to evaluate lung function in CF.

Actigraphy: Exercise tolerance can be affected by a number of factors, including activity level. In this study, subjects' activity levels will be monitored by actigraphy to determine whether subjects' activity increased with LUM/IVA treatment and to examine the relationship between physical activity and changes in exercise tolerance. Actigraphy will also be used to capture sleep/wake data, which reflect both functional and physiological health of subjects. The actigraph device can capture continuous sleep/wake data over a long period of time, is a cost-effective and minimally invasive in-home alternative to other methods to measure these behaviors (e.g., polysomnography), and offers a level of accuracy and reliability that cannot be achieved through subjective reports.

BMI: Malnutrition is common in patients with CF because of increased energy expenditures due to lung disease and fat malabsorption. Improved nutritional status, defined as an increase in weight and/or BMI, is an endpoint that has been used in previous clinical studies of LUM/IVA therapy (Studies 103 and 104).

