12.3.3.2 Analysis of Secondary Efficacy Variables

Key Secondary Efficacy Endpoint:

The key secondary efficacy endpoint is the change from baseline in exercise duration during CPET at Week 24. The same analysis method as for the primary efficacy endpoint will be used, with change from baseline in exercise duration as the dependent variable. To control for multiplicity, the test for change in exercise duration will only be considered statistically significant if the 2-sided *P* value is 0.05 or less and the test for the primary endpoint also is statistically significant.

Other Secondary Efficacy Endpoints:

All other secondary efficacy endpoints will be analyzed in a similar fashion. No adjustment for multiplicity will be made for these endpoints. The other secondary endpoints are listed in Section 7.2.

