- For all efficacy parameters, if there are multiple measurements within a visit window, the record at the scheduled visit will be used. If there are no measurements at the scheduled visit, then 1) the record closest to the target day will be used; or 2) if there are multiple records with the same distance to the target day, the latest record will be used.
- For all safety parameters, if there are multiple measurements within a visit window, then 1) the record closest to the target day will be used; or 2) if there are multiple records with the same distance to the target day, the latest record will be used.

BMI will follow visit window rules for efficacy parameters when being considered as an efficacy endpoint.

Incomplete/Missing data will not be imputed, unless otherwise specified; i.e., all missing values will remain as missing in all statistical analyses and listings, unless otherwise specified. Missing post-baseline values will not be imputed for efficacy analysis conducted

using a mixed model for repeated measures (MMRM) approach, which makes use of all available data even if a subject has missing data at some post-baseline visits.

Outliers: No formal statistical analyses will be performed to detect and/or remedy the presence of statistical outliers.

Repeated Observations: Measurements recorded at different time points are defined as repeated observations. If an assessment has planned repeated measurements, then statistical summaries will present all planned time points, as appropriate.

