Appendix B Precisions of Summary for Continuous Variables

Continuous Variables

Table 12-2 Precision of Special Summary Statistics for CF Studies

Variables	Statistics	Decimal Places
CPET Related variables	Mean, LS mean, 95% CI	1
Percent Predicted FEV ₁	Mean, LS mean, 95% CI	1
CFQ-R	Mean, LS mean, 95% CI	1
BMI	Mean, LS mean, 95% CI	1
PHQ-8/GAD-7	Mean, 95% CI	1
Demographics	Mean, 95% CI	1
Actigraphy	Mean, 95% CI	1

The precision of the Safety Lab Data will follow the latest standard from the Biometrics Standardization Committee.

The precision of the measurement in raw data for other continuous variables will be used to determine the number of decimal places to present in tables, figures, and derived listings. Minimum and maximum values will be reported with the same precision as the units of measure. The mean and median will be reported to 1 greater decimal place, and the SD and SE will be reported to 2 additional decimal places.

Any values that require transformation to standard units (metric or International System [SI]) will be converted with the appropriate corresponding precision.

Appendix C Analysis Visit Window Mapping Rules for Safety and Pharmacodynamic and Actigraphy Measurements

Table 12-3 Visit Window Mapping Rules for Safety and Pharmacodynamic and Actigraphy Measurements

Assessments	Visit	Target Study Day	Visit Window (in study days)
• CPET related	Week 12	85	(1, 92]
•	Week 24	169	[93, 176]
• Spirometry	Safety follow up week 28	197	[177, 204]
•			
• CFQ-R/PHQ-8/GAD-7			
•			
• Weight and Height			
•			
• Vital Signs			
•			
• Actigraphy*			
•			
• Labs – Liver Function Test			

* Baseline actigraphy data will be the average of the corresponding actigraphy data 7 days prior to the Day 1 visit (Day -7 to Day -1). The same rule applies to actigraphy data collected at week 12 and week 24, where the average of the corresponding actigraphy data 7 days prior to the target day visit (target study Days 85 and 169 will be used for these two visits). Due to a window of ± 7 Days for each of these visits, the actual 7-day interval from which actigraphy data is used may vary from subject to subject.

Appendix D Coefficients for Hankinson and Wang Methods for Calculating Predicted Spirometry Parameters

Percent predicted FEV₁ is the ratio of FEV₁ (L) to the predicted FEV₁ (L), expressed as a percentage. The predicted FEV₁ (L) will be calculated using the Hankinson¹ and Wang² standards.

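### The SAP drops, without a stated reason, the Week 24 between-arm comparison the protocol plans for PHQ-8, GAD-7, physical activity and sleep duration; separately, its ppFEV1 model omits its own continuous baseline.

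*SAP*

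**What the plan says.** Protocol 7.2 lists PHQ-8, GAD-7, physical activity by actigraphy, and sleep duration and quality among the other secondary endpoints. Protocol 12.3.3.2 states: "All other secondary efficacy endpoints will be analyzed in a similar fashion". The method it refers to is in Protocol 12.3.3.1: an MMRM whose result is the Week 24 treatment effect from a contrast, with a 95% CI and two-sided P value.

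SAP 9.3.2.2.2 keeps that model for the CPET variables, ppFEV1, BMI and CFQ-R. For a second list, which includes PHQ-8, GAD-7, physical activity and sleep duration, it says: "Analysis of the following other secondary endpoints will be based on descriptive summary statistics only". The accompanying 95% confidence intervals are by treatment group. Table 12-2 in SAP Appendix B ("Precision of Special Summary Statistics for CF Studies") gives LS means for the modelled endpoints but only means and CIs for PHQ-8/GAD-7 and actigraphy.

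For the modelled endpoints the SAP's rule is that "for each of these secondary endpoints, their corresponding value at baseline will replace baseline" VO2max in the model. ppFEV1 is the one exception, on the ground that ppFEV1 "at baseline as a stratification factor has already been included in the model". SAP 9.3.1.2 shows that this factor has two levels, below 70 and 70 or above.

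**The concern.** The protocol needs a placebo arm because "subject activity may increase as a result of being involved in an exercise tolerance study" (8.2.1). It includes actigraphy to establish whether subjects' "activity increased with LUM/IVA treatment and to examine the relationship between physical activity and changes in exercise tolerance" (8.2.3). By that reasoning, the change within the LUM/IVA arm combines any drug effect with a participation effect, and only the difference from placebo separates them. The SAP plans no such difference. The second purpose of actigraphy is not served directly either: the visible correlation list in SAP 9.3.2.3 pairs activity with ppFEV1, not with an exercise measure.

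The four endpoints also leave the framework that SAP 9.1 favours for missing data, the MMRM, "which makes use of all available data even if a subject has missing data at some post-baseline visits". A difference worked out later from the by-arm means would be unplanned, unadjusted and limited to observed cases.

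The ppFEV1 point is different in kind. It is an inconsistency inside the SAP, not a departure from the protocol, whose model has no own-baseline covariate. A two-level factor does not carry all the information in a continuous baseline, so some precision is given up for no benefit.

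**Working it through.** **1. Side-by-side reading.** Protocol: model, contrast, CI and P value for every other secondary efficacy endpoint. SAP: by-arm description for four of them. SAP section 3 records no modifications. The SAP introduction mentions added analyses but no removed ones, and 9.3.2.2.2 gives no reason.

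**2. The plan's own figure.** The documents state no power or precision for these endpoints. The only stated size is 33 per arm for the primary (difference 7.5%, SD 10%, two-sided 0.05, 80% power, 10% dropout; Protocol 12.1, SAP 7.2). A two-sample t-test needs 29 evaluable per arm (power 80.1%), and 29/0.90 = 32.2, rounded up to 33. The same method reproduces all six rows of the protocol's Table 12-1: 72, 59, 50, 44, 38, 33. So the numbers available are sound: 33 × 0.90 = 29.7, about 30 evaluable per arm.

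**3. Precision of a between-arm difference, in SDs of change, 30 per arm.**
- Unadjusted half-width: t(0.975, 58) × √(2/30) = 2.002 × 0.2582 = **0.517**.
- Own-baseline adjustment multiplies the variance by (1 + ρ)/2, where ρ is the baseline-to-Week 24 correlation and the variance is assumed equal at the two times.

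| Assumed ρ | Variance factor | Half-width |
|---|---|---|
| 0.5 | 0.75 | 0.517 × √0.75 = 0.448 |
| 0.7 | 0.85 | 0.517 × √0.85 = 0.477 |
| 0.9 | 0.95 | 0.517 × √0.95 = 0.504 |

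**4. What happens if readers compare the two by-arm intervals by eye, 29 per arm.** Each half-width is t(0.975, 28)/√29 = 0.380 SD, so intervals that just fail to overlap are 2 × 0.380 = 0.761 SD apart. Dividing by √(2/29) = 0.2626 gives t = 2.90 and P of about 0.005. At a true difference of 0.75 SD this informal rule succeeds about 49% of the time, against 80% for the planned type of test.

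**5. ppFEV1.** Eligibility limits FEV1 to 40–90% of predicted (Protocol 9.1). The spread within that range is an assumption. The split at 70 explains 72% of baseline variance if baseline is uniform on 40–90, and 64% if it is normal (mean 65, SD 14) truncated to that range.
- Residual variance with the split only: s²(1 − ρ²) + (1 − ρ)² × within-stratum variance.
- Residual variance with the continuous baseline: s²(1 − ρ²).
- Uniform case: s² = 50²/12 = 208.3; within-stratum variance = 0.28 × 208.3 = 58.3.
  - ρ = 0.9: 39.58 + 0.01 × 58.3 = 40.17, against 39.58, a reduction of 1.5%. The SE of the difference, √(2 × variance/30), goes from 1.636 to 1.625 points.
  - ρ = 0.8: 75.00 + 0.04 × 58.3 = 77.33, against 75.00, a reduction of 3.0%. The SE goes from 2.271 to 2.236 points.
- Truncated-normal case: reductions of about 1.9% and 3.8%.
- Across both cases the SE falls by 0.7–1.9%. At the much lower ρ = 0.5 the variance reduction would be 8.5–10.7%.

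**6. Sleep quality.** It is in Protocol 7.2 and is absent from the visible endpoint lists in SAP 6.1.2 and 9.3.2. No arithmetic applies.

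**The case against.** The strongest reply has five parts.

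- **The protocol section is only a summary, and detail is left to the SAP.** True, but a by-arm description with no model, contrast or between-arm estimate is a different analysis, not a detail of the same one.
- **Both arms are shown side by side, so the placebo change is visible and a crude difference can be derived.** This stands in part: the information is not lost. What is lost is a pre-specified, adjusted estimate, and comparing intervals by eye is a poor substitute (step 4).
- **The precision gain in step 3 comes from a baseline covariate the protocol never planned.** Correct. It shows what the SAP's own rule would give these endpoints, not the cost of leaving the protocol. It also shrinks as the correlation rises, to 5% of variance at 0.9.
- **The missing-data loss is limited.** This also stands in part. Questionnaires are repeated at the Early Termination visit, SAP 9.3 includes data after discontinuation, and the Week 24 window runs from day 93 to day 176. With two post-baseline visits, the MMRM adds only subjects with a Week 12 value and no Week 24 value.
- **The ppFEV1 omission is small, explained and unbiased under randomisation, and sleep quality may lie in blacked-out text.** All fair. The first is a minor improvement and the second is a query. Table 12-2 sets decimal places, so it supports the reading of SAP 9.3.2.2.2 but does not establish it alone.

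**Conclusion.** The concern holds. For PHQ-8, GAD-7, physical activity and sleep duration the SAP removes a comparison the protocol plans and gives no reason. For activity, the remaining summary does not directly answer the question the protocol asks.

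The consequence is confined to secondary endpoints that Protocol 12.3.3.2 leaves without multiplicity adjustment. The primary and key secondary conclusions do not change, and ppFEV1, BMI and CFQ-R keep a modelled comparison. A between-arm interval of about ±0.45 to ±0.52 SD of change is attainable, depending on adjustment and on a correlation the documents do not give.

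The ppFEV1 omission costs about 1.5–3.8% of residual variance at assumed correlations of 0.9–0.8. It causes no bias, and correcting chance imbalance in baseline is this same gain, not an extra one. Sleep quality is an unreconciled difference between the visible texts, with no size to attach.

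**What to change.** - **Four endpoints.** In SAP 9.3.2.2.2, run the same MMRM for PHQ-8, GAD-7, physical activity and sleep duration, each with its own baseline as covariate. Report the Week 24 LS mean difference with a nominal 95% CI. Treat time above sedentary, which the SAP added, the same way for consistency. If skewed scores are the reason for avoiding a model, say so and still give a between-arm difference with a CI, for example by bootstrap. Record the change and its reason before unblinding. A note alone would settle the discrepancy but would leave the activity question unanswered.
- **ppFEV1.** Add continuous baseline ppFEV1 to its models and keep the two-level factor.
- **Sleep quality.** Name a metric, or state that the endpoint is withdrawn and why.

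The first two changes cost a few model runs, some SAP wording and LS-mean entries in Table 12-2. The data are already scheduled at baseline, Week 12 and Week 24, and neither sample size nor alpha changes. The third needs a definition, since the protocol gives none, or one line.
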